MRI [Sessions]. [The MRI study will take the form of a two-session experiment, in which alcohol or placebo beverages are administered to each participant in a counterbalanced order. In Session 1,] participants will arrive at VCU's Collaborative Advanced Research Imaging (CARI) facility where they will repeat the screening procedures and then will practice the computer tasks that they will perform in the scanner. Then, participants will be told that they will receive [either] a placebo [or] an alcoholic beverage, but that they will not be informed of the nature of each beverage until the end of the study (see Figure 4 for the MRI scan timeline). [By random assignment,] participants will then consume [either a placebo beverage of orange juice with 4ml ethyl alcohol added to the rim or an alcoholic beverage

consisting of a 1:5 ratio of 95% ethyl alcohol and orange juice. The alcohol dose will be proportional to participants' body weight and sex, due to sex differences in body fat composition and alcohol metabolism (females: 0.9 g/kg ethyl alcohol; males: 1.0 g/kg ethyl alcohol). This alcohol dose typically increases participants' breath-alcohol-concentration to .08%, the legal driving limit in Virginia.] After consuming the beverage, participants will then be placed in the MRI scanner and complete a validated laboratory aggression paradigm that allows individuals to "hurt" a fictitious opponent with an aversive noise blast, while undergoing echo-planar functional MRI (EPI). In this task, participants compete against an opponent to press a button faster, and the loser of the competition then hears an aversive noise blast. Aggression is operationalized as the

Figure 4. Timeline of both MRI sessions.

volume of the noise blast (65-105 decibels) that participants select for a fictional opponent who repeatedly provokes them by selecting extremely loud noise blasts. After completing these scans, [participants will leave and return to the CARI center 7 days later for Session 2. Participants will consume either a placebo (if they consumed an alcoholic beverage in Session 1) or an alcoholic beverage (if they consumed an alcoholic beverage in Session 1), and then will be returned to the scanner to complete the aggression paradigm a second time against a new provocative opponent.] Participants will be told that both of their opponents are same-sex VCU undergraduates, when in fact, they are computer programs.

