**Figure 6. Anticipated results comparing polygenic risk groups on their aggressive behavior, after alcohol or placebo.**

[figure not shown]

the task. Multiple comparisons corrections will be conducted using nonparametric threshold-free cluster enhancement. Mediation models will then be fit in which the effect of polygenic risk score group on aggression (after the alcohol administration) will be mediated by functional and structural brain estimates from brain regions that were significantly different between the two polygenic risk groups (Figure 8). The PROCESS macro for SPSS will be used to conduct nonparametric bootstrapping (using 5,000 bootstrapped resamples) to test the significance of each neural mechanism's indirect effect.

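### The readable mediation text has no session-order covariate, so drink order can confound the brain-to-aggression path for functional mediators

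*Combined protocol and SAP*

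**What the plan says.** The MRI Sessions paragraph of Phase II states that "alcohol or placebo beverages are administered to each participant in a counterbalanced order", with the Session 1 drink set by random assignment. It continues: "participants will leave and return to the CARI center 7 days later for Session 2", when they "complete the aggression paradigm a second time against a new provocative opponent". (The sentence allocating the Session 2 drink names the same Session 1 condition for both branches. It must be reconciled with the counterbalancing statement. I read the design as a two-period crossover.)

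The mediation sentences in the Phase II Analytic Plan concern "the effect of polygenic risk score group on aggression (after the alcohol administration"). That effect is to be "mediated by functional and structural brain estimates from brain regions that were significantly different between the two polygenic risk groups". The test is "nonparametric bootstrapping (using 5,000 bootstrapped resamples) to test the significance of each neural mechanism's indirect effect", run in PROCESS. These sentences name no covariate and do not say which session or contrast supplies the brain estimates. The matching factors under Potential Problems and Alternative Strategies are age, sex, race and socioeconomic status; session order is not among them.

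The description of the mixed-effects GLM breaks off in the extracted text, and Figure 8, which draws the mediation models, is not shown.

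**The concern.** Under counterbalancing, alcohol-session aggression is measured at the first scan for some participants and at the second for the rest. By the second scan a participant has already done the task and been provoked by one opponent. Practice, habituation or growing suspicion could change both task activation and the volume chosen.

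Randomising order makes it independent of risk group, so the group-to-brain path and the total group effect are protected. It does not make order independent of the brain measure or of aggression. A variable that moves both is a common cause of mediator and outcome, and balancing it across risk groups does not remove it from the brain-to-aggression slope. The indirect effect is the product of the two paths, so bias in the slope is multiplied by the group-to-brain effect. Because mediators are restricted to regions that differ between the groups, that effect is non-zero in the sample. At stake is the test of Hypothesis 4, that brain changes carry the genetic effect.

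**Working it through.** **The plan's own figure.** The Phase II power analysis gives 198 analysable participants (99 per group) for at least 80% power at an indirect effect of 0.09%; 198 + 4 expected to be suspicious = 202, which is correct. The 198 cannot be reproduced from stated inputs, because no alpha, path coefficients or SDs are given for it. This point does not depend on it; 198 is used below only as the sample size.

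**Inputs.** From the documents: n = 198, two groups of 99, random counterbalanced order. Assumed: 1:1 order (p = 0.5), residual SDs of 1, group-to-brain effect a = 0.4 SD, direct group effect 0.2 SD, and a range of order effects gM (on the brain measure) and gY (on aggression), in SD units.

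**Model.** With X = risk group, O = order (0/1), M = brain measure and Y = alcohol-session aggression:

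- M = aX + gM·O + error
- Y = c′X + bM + gY·O + error

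Leaving O out of the second equation shifts the slope b by

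bias(b) = p(1−p)·gM·gY / [1 + p(1−p)·gM²], with p(1−p) = 0.25,

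and the indirect effect by a × bias(b).

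**Numbers put in, gM = gY = g:**

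- g = 0.2: 0.0100/1.0100 = 0.0099; × 0.4 = 0.0040
- g = 0.3: 0.0225/1.0225 = 0.0220; × 0.4 = 0.0088
- g = 0.5: 0.0625/1.0625 = 0.0588; × 0.4 = 0.0235
- g = 0.8: 0.1600/1.1600 = 0.1379; × 0.4 = 0.0552

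If gM = 0 or gY = 0, the slope bias is 0. If a = 0, the bias in the indirect effect is 0.

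**Simulation check.** 20,000 runs per row, order balanced within each risk group. Joint significance of both paths (two-sided 0.05) stands in for the bootstrap.

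| gM, gY | Mean indirect effect, true 0, no order term | False positives, no order term | False positives, order term | Mean indirect effect, true 0.080, no order term | Same, order term |
|---|---|---|---|---|---|
| 0, 0 | 0.0001 | 4.0% | 3.9% | 0.0801 | 0.0801 |
| 0.2, 0.2 | 0.0039 | 4.2% | 3.9% | 0.0841 | 0.0798 |
| 0.3, 0.3 | 0.0086 | 4.7% | 4.0% | 0.0896 | 0.0800 |
| 0.5, 0.5 | 0.0244 | 10.6% | 3.7% | 0.1049 | 0.0798 |
| 0.8, 0.8 | 0.0565 | 38.2% | 3.8% | 0.1384 | 0.0800 |
| 0.5, −0.5 | −0.0244 | 10.9% | 4.1% | 0.0571 | 0.0801 |
| 0, 0.5 | 0.0001 | 4.0% | 3.9% | 0.0805 | 0.0805 |

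The simulated means agree with the formula to about 0.001. With no order effect, power for the true indirect effect of 0.080 is 63.4% without the term and 63.2% with it.

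**The case against.** The strongest reply is that the effect may be negligible. The documents give no order effect, and pre-scan practice, a new opponent and a 7-day gap may all keep it small. Up to about 0.3 SD the false-positive rate stays within a percentage point of the 4.0% seen with no order effect. At 0.5 SD the slope bias of 0.06 is still below the slope's standard error of about 0.07 (1/√198). The bias also needs order to move both variables. All of this stands, and it limits the size of the point. It does not argue against a covariate that costs almost nothing.

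Four stronger readings are tempting, and the documents do not support them.

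- A reader might infer that the brain measures also come from the alcohol session only. The text ties only the outcome to alcohol; the functional estimate could already be an alcohol-versus-placebo contrast.
- A reader might infer that the plan has no order term anywhere. The GLM text and Figure 8 are unavailable, so the claim stops at the readable mediation text.
- A reader might infer that the placebo session goes unused. The Figure 6 caption compares the risk groups after either drink, so it enters the behavioural comparison. Hypothesis 4 does not require mediation of a difference score.
- A reader might infer that every mediator is affected. The practice argument concerns task activation; nothing in the plan suggests that drink order would shift DTI or T1 measures.

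Replacing the outcome with the alcohol-minus-placebo difference would not be a safe repair by itself. It changes the estimand, and its variance 2σ²(1−ρ) exceeds σ² when the between-session correlation ρ is below 0.5. A period effect π separates the two order groups by π in alcohol-session data, but by 2π in the difference (τ + π against τ − π, with τ the alcohol effect). Without an order term, differencing enlarges the confounding.

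**Conclusion.** The point holds for functional mediators, conditionally. As far as it can be read, the mediation model leaves out a known randomised design factor that may be a common cause of mediator and outcome, and counterbalancing across risk groups does not protect that path. The distortion is negligible for joint order effects up to about 0.3 SD and material from about 0.5 SD. At 0.5 SD a true indirect effect of 0.080 is estimated as 0.105, or as 0.057 if the two shifts have opposite signs.

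These sizes rest on assumed order effects, a = 0.4 SD, 1:1 order and a joint-significance test in place of the bootstrap; the documents supply none of the effect sizes. That structural mediators are little affected is also an assumption. Risk-group effects are not biased, only somewhat noisier. This is an inexpensive improvement that should be made, not evidence that the planned result would be wrong.

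**What to change.** - Add session order (alcohol first or second) as a covariate in both mediation equations. In the aggression equation it removes the confounding; in the brain equation it removes noise. The cost is one degree of freedom in each, with no new data and no change to the 198.
- State which session or contrast supplies each functional mediator, and which session supplies the DTI and T1 measures.
- As an additional analysis, adjust alcohol-session aggression and task activation for their placebo-session values, keeping the order term. This helps separate an alcohol-specific pathway from general aggressiveness and uses data already collected.
- Reconcile the Session 2 drink-allocation sentence with the counterbalancing statement, so that the order variable can be coded without ambiguity.

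No change to the mixed GLM is requested, because its terms cannot be read.

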**Aim 4: Identify functional and structural brain mechanisms that transmit the genetic effects on alcohol-influenced aggression.** *Hypothesis 4:* Polygenic risk scores for alcohol-influenced aggression will be associated with greater laboratory aggression, through changes in brain structure and function.

This proposal capitalizes on the resources available through [NIH-funded publicly-available datasets from the database of Genotypes and Phenotypes (dbGaP)] and VCU's Spit for Science (S4S) project, on which my primary mentor, [name] is a Principal Investigator. Drs. [name] and [name] (Co-Mentors) also play substantial roles in many of these projects. I would begin by analyzing existing data from [the dbGaP discovery sample], then seeking to replicate these findings with ongoing data collection for Spit for Science at my current institution, VCU. Finally, I would conduct a new MRI brain imaging study, using S4S participants (recruited based on their underlying genetic risk profiles) analyses in order to leverage my existing skillset in neuroimaging and laboratory aggression measurement and further accomplish the proposed research aims.

Accomplishing these aims would advance my long-term goal to become an independent alcohol investigator who integrates across multiple disciplines to study the factors that influence alcohol-influenced aggression. These activities would set the stage for R01-level applications to investigate the environmental factors that influence these effects, and biologically-informed interventions that might ameliorate them.

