**Figure 8. Mediation models that will be fit to the S4S sample, with brain data articulated as mediators.**

**Figure 7. Brain regions expected to be modulated by polygenic risk for alcohol-related aggression. Red = reward circuit, blue = prefrontal control circuit.**

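### For functional mediators taken from the same task run as the aggression outcome, a significant indirect effect cannot show that the brain region transmits the genetic effect rather than responding to the aggression

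*Combined protocol and SAP*

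**What the plan says.** Aim 4 (Specific Aims) is directional: "Identify functional and structural brain mechanisms that transmit the genetic effects on alcohol-influenced aggression".

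The Phase II description of the MRI sessions has participants do the competitive task "with an aversive noise blast, while undergoing echo-planar functional MRI (EPI"). The outcome is the "volume of the noise blast (65-105 decibels) that participants select for a fictional opponent" in that task. The surviving text describes no other functional run. DTI and T1 images are separate scans made after the task.

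The Phase II analytic plan (text between Figures 6 and 8) specifies models in which "the effect of polygenic risk score group on aggression (after the alcohol administration) will be mediated by functional and structural brain estimates". It takes as mediators estimates from "brain regions that were significantly different between the two polygenic risk groups", after threshold-free cluster enhancement for multiple comparisons. It then uses "nonparametric bootstrapping (using 5,000 bootstrapped resamples) to test the significance of each neural mechanism's indirect effect". The outcome is aggression after alcohol, and the Figure 8 caption has the models fitted "with brain data articulated as mediators". Summary and Future Directions speaks of functional responses to aggression following alcohol, which points to the alcohol run as the source of the functional estimate.

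**The concern.** The bootstrap tests whether a × b is zero, where a is the group difference in the brain estimate and b is the brain-aggression association given group. If activity and volume are recorded in one run, b has no direction. Suppose risk group raises aggression, and choosing and delivering louder blasts raises activity in a reward or control region. Then a and b are both non-zero, and the test rejects although the region transmits nothing. Matching on age, sex, race and socioeconomic status does not help, because this is not confounding by those variables.

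At stake is the functional half of Hypothesis 4, including the ventral striatum, the region on which the power analysis rests. A region could be named a mechanism when its activity follows from the behaviour it is said to explain.

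**Working it through.** **Sample size.** From the Phase II power analysis: 2 × 99 = 198 analysed, 198 + 4 expected exclusions for suspicion = 202 recruited, 101 per group. This reproduces. The 198 itself cannot be re-derived, because the path values and alpha behind it are not given. Only n = 198 is used below.

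**Assumptions.** None of these values is in the documents: a two-sided 5% test; group effect on aggression d = .3, .5, .8; within-group brain-aggression correlation r = .2, .3, .5.

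**Reversed model.** Aggression Y has a group difference d in within-group SD units. Brain activity is M = rY + √(1 − r²)·noise. There is no path from M to Y, so the true indirect effect through the brain is zero.

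**Closed-form approximation.**
- Path a: the group difference in M is r·d, so its z-statistic is centred on λ = r·d·√(99/2) = 7.036·r·d.
- Path b: by Fisher's z, the statistic is centred on κ = atanh(r)·√(198 − 1 − 3) = 13.93·atanh(r).
- Rejection is approximately power(λ) × power(κ), where power(x) = Φ(x − 1.96) + Φ(−x − 1.96).

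Power for b is .806 at r = .2, .991 at r = .3 and about 1 at r = .5. For d = .5 and r = .3: λ = 7.036 × .15 = 1.055, power for a = .184, and .184 × .991 = .182.

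| d | r = .2 | r = .3 | r = .5 |
|---|---|---|---|
| .3 | 6% | 10% | 18% |
| .5 | 9% | 18% | 42% |
| .8 | 16% | 39% | 80% |

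Simulation at 99 per group gives 5-18%, 9-42% and 16-79% for the three rows. A percentile bootstrap with the plan's 5,000 resamples gives 38% and 81% at d = .8 for r = .3 and .5. With d = 0 and r = .5 it rejects in 4%, and with r = 0 and d = .4 in 0.3%. The excess therefore needs both a group effect on aggression and an effect of aggression on the brain.

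**Effect of the region screen.** The plan corrects its group comparison, but no per-region threshold can be derived from the text. At d = .5 and r = .3, simulation with assumed thresholds of .05, .01 and .001 gives 17%, 5% and 1%. The formula, with 2.576 and 3.291 as critical values for a, gives 18%, 6% and 1%. These are rates for one region; a search over many regions would raise the chance of at least one such finding.

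**Swapping mediator and outcome does not settle direction.** At d = .8 and r = .5, under the reversed path the planned model rejects in 81% and the swapped model in 99.8%. Under true mediation the figures are 100% and 81%. Both models reject in 81% of studies either way.

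**Time-ordered model.** This uses first-half activity, second-half volume and first-half volume as a covariate. Under the reversed path:
- If activity depends on the observed first-half volume, false rejection is 0.2-2.4%.
- If activity follows an underlying aggressive state that volume measures with error, it is 3.5-26% across the settings tried with the covariate in both equations, and 13-81% with it in the outcome equation only.
- In one assumed forward scenario, power falls from 96% (same-run model) to 58%.

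**The case against.** The strongest reply has four parts.

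1. *The size rests on assumed values.* This stands. The documents give neither d nor r, call the discovery and replication datasets underpowered, and plan for a small indirect effect. At d = .3 and r = .2 the rate is about 5%, so there may be little inflation.
2. *The plan's own screen reduces the rates.* This stands for a single region, as shown. It does not restore direction: the screen tests only whether groups differ in activity, which both orders predict. A reader might take the 91-100% of screened regions that then give a significant indirect effect (r of .3 or more) as a false-positive rate. It is not one. Once a is significant, b nearly always is at this sample size, under true mediation as well.
3. *The sentence defining the functional contrast is lost.* This stands. A reader might infer that the plan has no time ordering within the task; that cannot be asserted of the full plan. A decision-phase or provocation contrast would change how far activity could result from the blast. If the mediator came only from the placebo run, false rejection in the cases checked (r = .5) drops to 0.2-0.5%, or 3-5% if aggression in the two runs correlates .5, provided the groups do not differ in placebo-run aggression. Summary and Future Directions points to the alcohol run.
4. *Unidentified direction is a general limit of mediation from concurrent data.* True, but Aim 4 claims transmission, and the surviving text attaches no caution to that claim.

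**Conclusion.** The point holds for functional mediators, on the reading that activity and volume come from the same alcohol-session run. A significant indirect effect there fits both orders and cannot establish that the region transmits the genetic effect. Under a fully reversed path the rejection rate runs from about 5% to 79% over the assumed d and r, before any allowance for a stricter screen. It approaches the upper end only with a large group effect and a strong brain-aggression correlation.

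Three stronger readings are not supported. The planned model is not unusable: it remains a valid description of association. The structural mediators do not share the problem in this form, because DTI and T1 are separate scans and not activity recorded during the choices. And a significant time-ordered model would not license a directional claim, because it can still reject falsely when activity follows an underlying aggressive state.

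**What to change.** In the Phase II analytic plan, beside the mediation models:

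1. State which run and which task event supply the functional estimate.
2. State that a significant indirect effect for a same-run functional estimate will be reported as an association among risk group, brain response and aggression, consistent with mediation but not evidence that the region transmits the genetic effect. Align the conclusion for Aim 4 with this.
3. Add, as a sensitivity analysis only, a time-ordered model: activity from the first half of the alcohol-session task, volume in the second half as outcome, and first-half volume as a covariate in both the mediator and the outcome equations. State that it reduces but does not remove the reverse-direction explanation.

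The cost is a weaker mechanistic conclusion for functional mediators and one extra, lower-powered analysis of data already planned. Data collection does not change.

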#### Feasibility

I have performed numerous functional and structural MRI experiments using these laboratory aggression procedures and statistical techniques. [My lab has also completed a complex MRI study using this aggression paradigm, which recruited 112 participants over 1 year, suggesting that

*[the large MRI sample size in this proposal can be readily obtained at VCU.]* Prior research using this laboratory aggression paradigm has shown that aggression on this task is reliably increased by alcohol administration and can be safely and effectively administered in the MRI scanner. Therefore, this task is well-adapted for the MRI environment, and for alcohol administration.

Power analysis. FMRIPower v1.0^67 [and powerMediation] packages were used to analyze pilot fMRI data from previous research on differences between groups (that are at-risk for aggression) in aggression-related brain activity. Using the ventral striatum (a core node of the brain's reward circuit) as the region-of-interest, [mediation modeling will have at least 80% power to detect a small indirect effect (0.09%) between risk groups with 198 participants, 99 per group. Based on previous work with this aggression paradigm, 4 of these participants will likely be suspicious of our deception. As such, a sample size of 202 participants was selected (101 per group).]

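### Mediators are chosen by their group difference and then tested in the same participants, so selected indirect effects are biased upward and the stated 80% power, which is for one fixed region, leaves out the selection step

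*Combined protocol and SAP*

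**What the plan says.** Hypothesis 4 (Specific Aims, Aim 4) is a mediation claim: polygenic risk raises laboratory aggression through changes in brain structure and function. The Phase II Analytic Plan tests it in two steps.

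- **Group comparison.** "Multiple comparisons corrections will be conducted using nonparametric threshold-free cluster enhancement". The readable text gives neither the search volume nor the significance level.
- **Mediation.** "Mediation models will then be fit in which the effect of polygenic risk score group on aggression" after alcohol is mediated by functional and structural measures taken from "brain regions that were significantly different between the two polygenic risk groups". PROCESS with 5,000 bootstrap resamples is then used "to test the significance of each neural mechanism's indirect effect".

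The Figure 8 caption describes "Mediation models that will be fit to the S4S sample, with brain data articulated as mediators", and the S4S sub-sample is the only imaging sample the study collects. The readable text mentions no hold-out sample, data split, cross-validation, fixed list of mediators or correction across mediators. The Figure 7 caption labels two circuits in which effects are expected ("Red = reward circuit, blue = prefrontal control circuit"), but the mediation rule selects by significance and not from that figure.

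The power paragraph under Phase II Feasibility works from a single region. Its sample-size sentence begins "Using the ventral striatum (a core node of the" reward circuit). It gives at least 80% power for an indirect effect of 0.09% with 198 participants, 99 per group, and adds 4 for suspicion to reach 202.

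**The concern.** An indirect effect is the product a×b. Here a is the risk-group difference in the brain measure, and b is the slope of aggression on that measure given group. Choosing regions because the estimate of a is significant keeps those where chance pushed a upward. Estimating a×b in the same people carries that chance excess into the result. TFCE limits how many regions are falsely declared different. It does not shrink the estimates in the regions that pass. The bootstrap starts after selection and does not repeat it, so its intervals ignore it.

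The power statement has a related gap. Under the plan a region's mediation is tested only if the region first passes the corrected group comparison. The 80% has no such step, yet it justifies the sample size. At stake are the reported size of any mediation effect and the chance that a real mediator with a modest group difference is tested at all.

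The plan accepts the principle elsewhere. Under Phase II, Recruitment and Screening, it declines to build risk scores from the S4S GWAS because reusing the same individuals inflates associations. It does not carry this over to the choice of mediators.

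**Working it through.** **1. The plan's own figures.** 198 + 4 = 202 reproduces. The 80% can be neither reproduced nor refuted, because alpha, sidedness, the a and b paths and the scale of the 0.09% are not given. Read as 0.09% of variance (R² = 0.0009), two-sided power at N = 198 and .05 is about 6%. Read as a standardized product a×b = 0.09, it depends on the split: a = b = 0.3 gives 86% (Sobel) or 98% (both paths significant), while a = 0.5, b = 0.18 gives 57% or 60%. The check below therefore concerns what selection does, not whether 80% is right for the fixed region.

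**2. Passing selection, and inflation of the a path.** The input from the documents is 99 per group. The true difference d (in SD) and the two-sided threshold are assumptions.

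- SE = √(2/99) = 0.1421 and m = d/SE.
- P(selected) = Φ(m − z).
- Inflation = mean selected estimate ÷ truth = 1 + φ(z − m) / [m·Φ(m − z)].

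For d = 0.4, m = 2.814. At .05 (z = 1.960), P = Φ(0.854) = 0.804 and inflation = 1 + 0.277/(2.814 × 0.804) = 1.12. At .001 (z = 3.291), P = Φ(−0.477) = 0.317 and inflation = 1 + 0.356/(2.814 × 0.317) = 1.40.

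| True difference | Threshold | Passes selection | a path inflated |
|---|---|---|---|
| 0.3 SD | .01 | 32% | 1.53-fold |
| 0.3 SD | .001 | 12% | 1.79-fold |
| 0.4 SD | .05 | 80% | 1.12-fold |
| 0.4 SD | .01 | 59% | 1.23-fold |
| 0.4 SD | .001 | 32% | 1.40-fold |
| 0.5 SD | .005 | 76% | 1.12-fold |
| 0.6 SD | .001 | 82% | 1.07-fold |

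**3. Power of the two-step procedure.** Assume standardized a = b = 0.2267, which gives 80% for one fixed region at N = 198 when both paths must be significant at .05. Then a/SE = 0.2267/√((1 − 0.0514)/196) = 3.26 and b/SE = 0.2267 × √195 = 3.17. The path powers are Φ(3.26 − 1.96) = 0.903 and Φ(3.17 − 1.96) = 0.886, and their product is 0.80. Now test a at .05/K for K effective independent searches, a Bonferroni stand-in for TFCE, and keep b at .05.

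| K | P(a passes) | × P(b) | Power | a path inflated |
|---|---|---|---|---|
| 1 | 0.903 | 0.886 | 80% | 1.06-fold |
| 2 | 0.845 | 0.886 | 75% | 1.09-fold |
| 10 | 0.674 | 0.886 | 59–60% | 1.16-fold |
| 100 | 0.412 | 0.886 | 36–37% | 1.29-fold |

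A simulation with the percentile bootstrap (1,000 resamples, 2,000 replicates per setting, a = b = 0.226) agrees: power 79% at K = 1, 58% at K = 10 and 36% at K = 100. The true a×b is 0.051. Its mean estimate is 0.051 without selection and 0.054, 0.059 and 0.067 after selection at K = 1, 10 and 100.

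**4. What the bootstrap still tests.** With a true 0.4 SD difference and selection at .001, the share of selected regions with a significant indirect effect is 4% at b = 0, 31% at b = 0.1, 78% at b = 0.2 and 98% at b = 0.3. With a = 0, b = 0.3 and selection at an uncorrected .05, 92% of selected regions give a significant indirect effect, but the overall rate of selected and significant is 4.7%.

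**The case against.** Three stronger readings are tempting, and the documents support none of them.

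- **That mediation becomes automatic once a region is selected.** This holds only if the brain-aggression slope is strong. Step 4 shows the share running from 4% to 98% as b goes from 0 to 0.3, and the documents give no slope. Selection largely settles the a path, while the b path is still tested.
- **That the plan will yield many false mediators.** The 92% in step 4 is conditional on an error that the correction is meant to make rare. If TFCE holds family-wise error, the overall rate of false mediators through a null a path stays near alpha.
- **That regions must survive a whole-brain search.** The plan names TFCE but, in the readable text, no search volume. Part of the Analytic Plan just before the TFCE sentence is not readable and may define a mask. The two circuits named under Figure 7 make a restricted search plausible, and with two effective searches power is 75% against 80%.

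It is also fair to say that the power paragraph openly ties its 80% to the ventral striatum, and that large group differences pass selection with little inflation (0.6 SD at .001: 82%, 1.07-fold).

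These points limit the size of the problem but do not remove it. A mask would change the number of searches, not the rule that mediators are the regions that differ. Even a single region selected at .05 shows some upward bias.

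**Conclusion.** The point holds in a limited form. Indirect effects reported for significance-selected regions will be biased upward, and the planned TFCE and bootstrap do not correct this. The 80% power describes a fixed ventral striatum test, not the select-then-test sequence, and it omits the selection step by an amount that cannot be fixed from the documents. The scenarios in steps 2 and 3 run from slight (1.06-fold inflation with no power loss at K = 1) to serious (1.79-fold for 0.3 SD at .001; 36–37% power at K = 100). They rest on assumed true effects, assumed thresholds and Bonferroni as a stand-in for TFCE, so they are a range and not a corrected figure. A reader might also infer that the 80% is wrong for the ventral striatum itself. Its inputs are too incomplete to show that either way.

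**What to change.** In the Phase II Analytic Plan:

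- Name the ventral striatum, defined by an anatomical mask, as the primary mediator, and state which brain measure is used. Test its indirect effect whether or not the region differs between groups, so that the test matches the power calculation.
- Treat mediation in regions selected by group significance as secondary or exploratory, and report those estimates as subject to selection inflation.
- State the search volume and significance level for TFCE.

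In the power paragraph, say that the 80% applies only to the fixed ventral striatum test.

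The cost is wording, with no new data or participants. The downside is that mediation in unexpected regions becomes exploratory. Extending the primary list to many regions is not a free improvement. Under the step 3 assumptions, testing both paths at .05/10 = .005 for ten regions gives 0.674 × Φ(3.17 − 2.81) = 0.674 × 0.640 = 43%, against 59–60% for the planned sequence over the same ten. Figure 7 is not shown beyond its two circuit labels, so a region list could not be taken from it here in any case.
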